# **7 ADVERSE EVENTS AND SAFETY REPORTING**

## **7.1 Safety and Tolerability Assessments**

Safety and tolerability will be assessed on an ongoing basis by review of reported AEs, physical examinations, vital signs (including weight, seated SBP/DBP, and heart rate), and clinical safety labs (hematology, serum chemistry, and urinalysis).

## **7.2 Definition of Adverse Event**

An AE is defined in 21 CFR 312.32(a) as follows:

Any untoward medical occurrence associated with the use of a drug in humans, whether or not considered drug related.

An AE (also referred to as an adverse experience) can be any unfavorable and unintended sign (e.g., an abnormal laboratory finding), symptom, or disease temporally associated with the use of a drug, and does not imply any judgment about causality. An AE can arise with any use of the drug (e.g., off-label use, use in combination with another drug) and with any route of administration, formulation, or dose, including an overdose.

AEs will be collected starting with Visit 2/Day -10. However, AEs occurring between Visit 2/Day -10 and Visit 3/Day 1 will be regarded as “pretreatment” if they occur before IP administration at Visit 3/Day 1. TEAEs are defined as any AE that starts or increases in severity after the first randomized dose of study IP on Visit 3/Day 1.

### 7.3 Definition of Serious Adverse Event

A SAE is defined in 21 CFR 312.32(a) as follows:

An AE is considered “serious” if, in the view of either the Investigator or Sponsor, it results in any of the following outcomes:

- Death;
- Life-threatening AE;
- Inpatient hospitalization or prolongation of existing hospitalization;
- Persistent or significant incapacity or substantial disruption of the ability to conduct normal life functions;
- Congenital anomaly/birth defect.

Important medical events that may not result in death, be life-threatening, or require hospitalization may be considered serious when, based upon appropriate medical judgment, they may jeopardize the subject and may require medical or surgical intervention to prevent one of the outcomes listed in this definition. Examples of such medical events include allergic bronchospasm requiring intensive treatment in an emergency room or at home, blood dyscrasias or convulsions that do not result in inpatient hospitalization, or the development of drug dependency or drug abuse.

An AE is considered “life-threatening” if, in the view of either the Investigator or Sponsor, its occurrence places the subject at immediate risk of death. It does not include an AE that, had it occurred in a more severe form, might have caused death.

#### 7.3.1 Adverse Events of Hypoglycemia

The CTCAE (version 4.0) definition for mild, moderate, and severe hypoglycemia based on blood glucose will be used, as shown below:

Mild: from 55 to <70 mg/dL (3.0 to <3.8 mmol/L)

Moderate: from 40 to <55 mg/dL (2.2 to <3.0 mmol/L)

Severe: from 30 to  $< 40$  mg/dL ( $1.7$  to  $< 2.2$  mmol/L)

Life Threatening:  $< 30$  mg/dL ( $< 1.7$  mmol/L)

Subjects with hypoglycemia will be provided with 2-4 glucose tablets as necessary until symptoms subside or blood glucose increases to greater than 70 mg/dL. If a patient has greater than 2 episodes of symptomatic hypoglycemia at any particular study visit, they will be terminated from the study.

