#### Secondary Endpoints

3. Glucodynamics over the final 10 days of each treatment period as measured by CGM:
  - a. Time in range 70 - 180 mg/dL
  - b. Time <70 mg/dL
  - c. Time >180 mg/dL
  - d. Time >250 mg/dL
  - e. Glucose Coefficient of Variation
  - f. Low Blood Glucose Index (LBGI)

- g. Glucose below 70 mg/dL Area Over the Curve (AOC70)
4. Total daily non-oral insulin requirements in units per kilogram (kg) body weight over the last 10 days of each treatment period.

Exploratory Endpoints:

5. HbA1c measured at the end of each treatment period
6. Patient dairy-reported carbohydrate intake over the final 10 days of each treatment period
7. Changes in body weight from baseline (Visit 2) to the end of each treatment period
8. Other measures of hypoglycemia:
  - a. Severe hypoglycemia (SH) events (impaired or loss of consciousness requiring assistance of another)
  - b. Documented symptomatic hypoglycemia (an event during which typical symptoms of hypoglycemia are accompanied by a measured plasma glucose concentration <70 mg/dL (3.9 mmol/L))
  - c. Total time <70 mg/dL by CGM
  - d. Nocturnal hypoglycemia, severe or documented symptomatic episodes (as defined above) occurring after the subject has retired for the primary sleeping period

Safety assessments evaluating:

- Changes in clinical laboratory tests (hematology, chemistry, urinalysis);
- Collection of adverse events (AEs);
- Changes in Vital signs measurements

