Events that may trigger premature termination of a study or closure of an Investigational Site include, but are not limited to, a new toxicity finding, a request to discontinue the trial from a regulatory authority, non-compliance with the protocol, GCP violations, slow recruitment/low enrollment, or change in development plans for the study treatment.

If either of the criteria listed below is met, enrollment of new subjects and dosing of ongoing subjects will be temporarily stopped. The Investigator, Sponsor, and the Medical Monitor will discuss whether a lower dose or any additional treatment guidelines should be implemented, or if the trial should be permanently stopped. Any proposed changes to the protocol to address such findings will be submitted for review and approval by the IRB and FDA prior to re-starting the trial.

1. A death within 30 days after study treatment administration where there is a reasonable possibility that the drug caused the event;
2. Two Grade 4 AEs where there is a reasonable possibility that the study treatment caused the events.

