#### 7.4.1 Routine Reporting of Adverse Events

All AEs, whether or not associated with the study treatment, that are observed by the Investigator, other Investigational Site personnel, or those reported by the subject will be recorded in the subject's source documentation and on the AE page of the eCRF. Copies of the SAE CRF pages or an SAE listing generated based on the eCRF pages will be submitted to the Sponsor at regularly scheduled intervals to allow the Sponsor to meet expedited regulatory reporting requirements under 21 CFR 312.32 (see Section 7.4.2 for further detail) and regular regulatory reporting requirements under 21 CFR 312.33.

For each AE, the following information will be entered in the eCRF:

- Medical diagnosis of the event in standard medical terminology (if a medical diagnosis cannot be determined, a description of each sign or symptom characterizing the event);
- Date of onset of any new AE or worsening of a previously observed AE;
- Date of resolution of the event (or confirmation ongoing);
- Whether the event is serious (per definition in Section 7.3), and if so, the reason it is considered serious;
- Severity of AE (per definition in Section 7.6);
- Assessment of the attributability of the AE to the study treatment (per definition in Section 7.5);
- Whether the event is expected (per definition in Section 7.7);
- Action taken in treating the AE (including concomitant medications or therapies administered) and/or change in the study treatment administration or dose (including whether the study treatment was temporarily interrupted or discontinued);
- Outcome of AE (per definition in Section 7.8).

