#### 7.6 Adverse Event Severity Assessment

The severity of each AE will be graded according to the NCI CTCAE, version 4.03. The severity of AEs that are not specifically listed in the CTCAE will be categorized according to the general guidelines provided in the CTCAE, and as summarized in the table below.

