##### General Guidelines for Severity Assessment of Adverse Events

Grade 1: Mild; asymptomatic or mild symptoms; clinical or diagnostic observations only; intervention not indicated.
Grade 2: Moderate; minimal, local or noninvasive intervention indicated; limiting age-appropriate instrumental activities of daily living (ADL) [preparing meals, shopping for groceries or clothes, using the telephone, managing money, etc.].

Grade 3: Severe or medically significant but not immediately life-threatening; hospitalization or prolongation of hospitalization indicated; disabling; limiting self-care ADL (bathing, dressing and undressing, feeding self, using the toilet, taking medications, and not bedridden).
Grade 4: Life-threatening consequences; urgent intervention indicated.
Grade 5: Death related to AE.

Note the distinction between the severity and the seriousness of an AE. A severe AE is not necessarily a SAE. For example, a headache may be severe (interferes significantly with subject's usual function) but would not be classified as serious unless it met one of the criteria for SAEs, listed above in Section 7.3.

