2.8. Efficacy Evaluations

The primary endpoints for the study are:

1. To compare the amount of basal, bolus and total (basal + bolus) exogenous insulin utilized over the final 10 days of each treatment period.
2. To compare the impact of Oral Insulin dosed QD to Oral Insulin dosed TID and associated adjustments of basal and bolus insulin on mean 24-hour CGM glucose levels during the final 10 days of each treatment period.

The secondary endpoints for the study are:

1. Glucodynamics over the final 10 days of each treatment period as measured by CGM:
 - a. Time in range 70 – 180 mg/dL
 - b. Time <70 mg/dL
 - c. Time >180 mg/dL
 - d. Time >250 mg/dL
 - e. Glucose Coefficient of Variation
 - f. Low Blood Glucose Index (LBGI)
 - g. Glucose below 70 mg/dL Area Over the Curve (AOC₇₀)
2. Total daily non-oral insulin requirements in units per kilogram (kg) body weight over the last 10 days of each treatment period.

The exploratory endpoints for the study are:

1. HbA1c measured at the end of each treatment period
2. Patient diary-reported carbohydrate intake over the final 10 days of each treatment period
3. Changes in body weight from baseline (Visit 3) to the end of each treatment period
4. Other measures of hypoglycemia
 - a. Severe hypoglycemia events (impaired or loss of consciousness requiring assistance of another)
 - b. Documented symptomatic hypoglycemia (an event during which typical symptoms of hypoglycemia are accompanied by a measured plasma glucose concentration <70 mg/dL)
 - c. Total time <70 mg/dL by CGM
 - d. Nocturnal hypoglycemia, severe or documented symptomatic episodes (as defined above) occurring after the subject has retired for the primary sleeping period.

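### Protocol 7.3.1 grades hypoglycemia by blood glucose alone, and nothing says whether it or CTCAE 4.03 governs, so clinically severe events may be under-graded

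*Protocol*

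**What the plan says.** Protocol 7.3.1 states that "The CTCAE (version 4.0) definition for mild, moderate, and severe hypoglycemia based on blood glucose will be used". The bands are mild 55 to <70, moderate 40 to <55, severe 30 to <40 and life threatening <30 mg/dL. Symptoms, consciousness and help from others play no part in them.

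Protocol 2.2 names as an exploratory endpoint "Severe hypoglycemia (SH) events (impaired or loss of consciousness requiring assistance of another", and SAP 2.8 does the same: "Severe hypoglycemia events (impaired or loss of consciousness requiring assistance of another". Neither sets a glucose limit.

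For the severity entered in the eCRF, Protocol 7.4.1 points to 7.6, which says: "The severity of each AE will be graded according to the NCI CTCAE, version 4.03". Protocol 8.6.2 repeats that version. The general guidelines in 7.6 describe Grade 4 as "Life-threatening consequences; urgent intervention indicated", but 7.6 reserves those guidelines for events that the CTCAE does not itself cover.

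Protocol 4.3 temporarily stops enrollment and dosing after "Two Grade 4 AEs where there is a reasonable possibility that the study treatment caused the events".

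SAP 2.7.2 commits to the share of patients with hypoglycemia in each regimen, taken from the Hypoglycemic / Hyperglycemic log. It mentions no split by type of event.

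**The concern.** Hypoglycemia is the adverse event that Protocol 7.5.1 names for ORMD-0801, and here the product is added to injected insulin in type 1 diabetes. Under the 7.3.1 bands, a subject who loses consciousness and needs help at 45 mg/dL ranks below a symptom-free subject with a reading of 35 mg/dL. Protocol 8.6.2 shows each subject at the worst severity for a given event, and SAP Table 14.3.1.5 tabulates severity, so the order could be reversed where QD and TID are compared on safety.

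The halt in 4.3 counts grades. Section 7.3.1 uses severity words and does not tie them to grades. It also does not say how to grade an event with no reading. A safety pause should not depend on how a site resolves that.

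**Working it through.** This is a question of definitions, and the plan has no figure to reproduce. The check applies the 7.3.1 bands to example events and compares the result with the clinical definition in Protocol 2.2 and SAP 2.8.

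**Step 1: classify.**

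| Event | Label under 7.3.1 | Severe under 2.2 / SAP 2.8? |
|---|---|---|
| No symptoms, 35 mg/dL | Severe | No |
| Assisted loss of consciousness, 25 mg/dL | Life threatening | Yes |
| Assisted loss of consciousness, 35 mg/dL | Severe | Yes |
| Assisted loss of consciousness, 45 mg/dL | Moderate | Yes |
| Assisted loss of consciousness, 55 mg/dL | Mild | Yes |
| Assisted loss of consciousness, no reading | None can be assigned | Yes |

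The two definitions part company over 40 to <70 mg/dL, which is two of the four bands.

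**Step 2: which rule governs?** Section 7.3.1 is specific to hypoglycemia and mandatory in tone. Section 7.4.1 nevertheless sends the recorded severity to 7.6 and so to CTCAE 4.03, while 7.3.1 cites version 4.0. No sentence gives either rule precedence. The clinical guidelines in 7.6 do not settle it: 7.3.1 attributes its bands to the CTCAE, so hypoglycemia is treated there as a listed event, and the guidelines are for unlisted ones. The CTCAE 4.03 entry for hypoglycemia is not reproduced, so its content cannot be used here.

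**Step 3: could a separate entry rescue the grade?** A site might record loss of consciousness as its own event. That is not the default, because 7.4.1 asks for the diagnosis and wants, only "if a medical diagnosis cannot be determined, a description of each sign or symptom characterizing the event". Hypoglycemia is a diagnosis.

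**Step 4: the halt.** Assume that the four bands mean Grades 1 to 4, which 7.3.1 does not say. Take two treatment-related events with life-threatening consequences, one at 25 and one at 35 mg/dL. The bands give one Grade 4 and one Grade 3, so the rule is not met. Graded on consequences, both are Grade 4 and the rule is met. The same gap exists for any such event at 30 mg/dL or above, or with no reading.

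**Step 5: size.** The documents give no frequency for these events. As a share of a regimen, one subject is 1/26 = 3.8% (SAP 2.11) or 1/24 = 4.2% (Protocol 8.1), assuming that every randomized subject receives that regimen. This is the weight of any single subject, not an estimate of how many would be misgraded.

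**The case against.** The strongest reply is that 7.4.1 sends the recorded severity to 7.6, not to 7.3.1. CTCAE 4.03 may contain a clinical criterion for hypoglycemia that would give the right grade. This stands in part. A reader might infer that assisted events at 40 to <70 mg/dL will certainly be tabulated as mild or moderate. The documents do not support that, because it holds only if 7.3.1 is followed. They do show two rules with no stated order between them.

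A second reply is that severity and seriousness are different things, as 7.6 itself notes. This stands. A reader might infer that the glucose bands contradict Protocol 7.3, where an event is life-threatening if "its occurrence places the subject at immediate risk of death". That definition is a criterion of seriousness, so it does not fix a severity grade. The case here rests on Protocol 2.2 and SAP 2.8, and for the halt on the missing link between the bands and Grade 4.

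A third reply is that the events are caught elsewhere. That is right. An event that meets a criterion in 7.3 is an SAE at any glucose value. It is reported within 24 hours, and the Investigator, Medical Monitor and Sponsor review it and can suspend the study. Clinically severe hypoglycemia is also an exploratory endpoint in its own right. None of this sets the grade, however, and the 4.3 trigger uses the grade.

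Finally, Table 14.3.4 may already split events by type. SAP 4.5 places the shells in a separate file, so this cannot be seen. The SAP text commits only to the overall share affected.

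**Conclusion.** The concern holds as a matter of possible under-grading. Section 7.3.1 gives clinical impairment no way to raise the severity of a hypoglycemia event, and nothing says whether it or CTCAE 4.03 governs. If 7.3.1 is followed, an assisted loss of consciousness in two of the four bands is graded below severe. An event with life-threatening consequences outside the lowest band, or without a reading, is not assured to count as Grade 4 for the halt.

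No event is lost, the AE comparison is descriptive, and no primary endpoint, sample size or error rate is affected. The number of subjects concerned cannot be derived from the documents. The conclusion assumes only that sites may follow the specific section, which its wording invites. The correction should be made because it is cheap and protects both the severity tables and the halt.

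**What to change.** In Protocol 7.3.1, state that:

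- the grade of a hypoglycemia event is the higher of its glucose band (mild, moderate, severe, life threatening = Grades 1 to 4) and its clinical grade;
- impaired or lost consciousness that needs another person's help is at least Grade 3, whatever the glucose value and also if none was taken;
- life-threatening consequences are Grade 4 on the same terms and count toward the halt in 4.3;
- this rule governs hypoglycemia under 7.6 and 8.6.2.

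Taking the higher of the two matters. If the bands applied only when there was no impairment, assisted unconsciousness at 25 mg/dL could fall from life threatening to a minimum of Grade 3, and impairment without assistance at 35 mg/dL would have no grade. With the higher-of rule these become at least Grade 4 and at least Grade 3, and assisted unconsciousness at 45 mg/dL rises from Grade 2 to at least Grade 3.

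In SAP 2.7.2 and Table 14.3.4, report the severe, documented symptomatic and nocturnal events already named in SAP 2.8 for each regimen, beside the overall percentage. Confirm that the log records glucose, symptoms, consciousness and assistance, since its fields are not in the documents.

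The cost is a few sentences and a few table rows. A temporary pause under 4.3 may come slightly earlier.

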Subjects will be provided with diaries at Visits 2, 4 and 6, and will be asked to capture the amount of basal and bolus exogenous insulin administered each day and calculate their carbohydrate count for all meals and snacks over the 10-day CGM monitoring period of each treatment period.

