### 3.9 Early Withdrawal (EW)

If a randomized subject is withdrawn from the study prior to completing study treatment, the subject will be discharged from the study after following procedures will be performed:

- Review of medications and supplements;
- Vital signs (including weight, seated SBP/DBP, and heart rate);
- Physical examination;
- Collect data from CGM monitor (if applicable);
- Collect and review diary (if applicable);
- Collection of fasted blood and urine samples for:

- Clinical safety labs, including hematology, serum chemistry (with fasting plasma glucose/FPG), HbA1c and urinalysis (see Section 6.3.5 for list of tests).
- Returning of IMP;
- Assessment of compliance to IMP;
- Adverse events will be monitored and recorded;
- Discharge from the study.

Any subject with a possible study treatment related AE at the time of EW will be followed until resolution or stabilization of the event.

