#### **4.3 Subject and Trial Discontinuation**

Subjects may choose to withdraw from this study at any time for any reason without penalty of jeopardizing their health care or loss of benefits to which the subject is otherwise entitled.

Within the provisions of informed consent and good clinical judgment with respect to safety, every attempt will be made to have subjects complete the study. The following are reasons to terminate a subject's participation in the study:

1. Subject experiences an AE that in the judgement of the Investigator poses a significant risk to the subject for continued participation in the study.
  - a. If a subject experiences hyperglycemia, defined in Section 7.3.2, blood glucose will be checked 1-2 hours later. If the glucose remains elevated, the subject will be withdrawn from the study.
2. Subject uses a prohibited medication (listed in Section 5.7) that in the judgment of the Investigator poses a significant risk to the subject for continued participation in the study or that will interfere with the interpretation of the results of the study.
3. Subject becomes pregnant.
4. Significant protocol violation or noncompliance on the part of the subject or the Investigator.
5. Intercurrent illness that requires treatment that is not consistent with the protocol requirements, or intercurrent illness or the associated treatment that in the judgment of the Investigator poses a significant risk to the subject for continued participation in the study.
6. Subject wishes to withdraw for any reason.
7. Sponsor elects to end the study, or the Investigational Site elects to end the study at their site.
8. Any other reason that in the judgment of the Investigator poses unacceptable risk to the subject.

Reasons for study drug discontinuation may include the following:

1. Adverse event
2. Episodes of hypoglycemia as defined in Section 7.3.1.
3. Subject meets one of the exclusion criteria during the study
4. Any clinically significant change in the subject's medical condition

Subjects who withdraw from the study prior to treatment may be replaced. Subjects who are withdrawn and have received at least one treatment will not be replaced. Subjects who discontinue study drug treatment will not be replaced.

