Except in cases of emergency, the Investigator should consult with the Sponsor and the Medical Monitor before removing the subject from the study. In some circumstances it may be necessary to temporarily interrupt treatment as a result of AEs that may have an unclear relationship to study treatment. The Investigator should obtain approval from the Sponsor and Medical Monitor before restarting study treatments that were temporarily discontinued for an AE.

In the event that a subject discontinues the study prior to completion, the date the subject is withdrawn and the reason for discontinuation will be recorded in the source documents and CRF. Although a subject will not be obliged to give his/her reason for withdrawing prematurely, the Investigator will make a reasonable effort to obtain the reason while fully respecting the subject's rights.

All subjects who are randomized and treated (i.e., received any amount of study treatment) will be included in the safety analyses. Thus, every effort will be made to contact any subject who fails to attend any appointments/contacts, in order to ensure that he/she is in satisfactory health. If a subject withdraws from the study as a result of meeting discontinuation criteria after the start of study treatment administration, reasonable efforts should be made to have the subject return for the early withdrawal evaluations (Section 3.9). Any subject withdrawn due to a suspected study treatment -related AE should be followed until resolution or stabilization of the event.

Subjects may choose to withdraw authorization to use and disclose their PHI as defined by the HIPAA. Such withdrawal of authorization must be made to the Investigator in writing. Any PHI collected by the Investigator prior to the date of such withdrawal will continue to be used and disclosed.

Randomized subjects who are discontinued from this study for any reason will not be replaced.

The Sponsor has the right to terminate this study, and the Investigator/Investigational Site has the right to close the site, at any time, although this should occur only after consultation between involved parties. The Investigator will notify the IRB in writing of a premature termination of a study or closure of Investigational Site and will send a copy of the notification to the Sponsor.

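### Section 7.3.1 lets glucose-tablet treatment end on symptom relief alone, with no repeat glucose; its per-visit stopping count also needs its meaning stated

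*Protocol*

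**What the plan says.** Protocol Section 7.3.1 grades hypoglycemia by glucose: mild from 55 to below 70 mg/dL, moderate from 40 to below 55, severe from 30 to below 40, and life-threatening below 30. It then sets two rules.

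- **Treatment.** Subjects receive 2 to 4 glucose tablets "as necessary until symptoms subside or blood glucose increases to greater than 70 mg/dL".
- **Stopping count.** "If a patient has greater than 2 episodes of symptomatic hypoglycemia at any particular study visit, they will be terminated from the study".

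Randomized dosing starts at Visit 3 (Day 1). The later scheduled visits are Visits 4 to 7 on Days 18, 28, 46 and 56, each a morning attendance (Sections 3.5 to 3.8). Capsules are taken at bedtime or before meals (Section 5.3), while subjects go on adjusting their own basal and bolus insulin (Section 3.1). Section 7.5.1 names hypoglycemia as a potential adverse event of ORMD-0801.

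Other routes to action are in Section 4.3:

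- Participation may be ended under item 1 ("Subject experiences an AE that in the judgement of the Investigator poses a significant risk") or item 8, any other unacceptable risk.
- Study drug may be discontinued for "Episodes of hypoglycemia as defined in Section 7.3.1" (item 2), for meeting an exclusion criterion during the study (item 3), or for a clinically significant change in condition (item 4).
- The whole trial pauses after "Two Grade 4 AEs where there is a reasonable possibility that the study treatment caused the events".

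**The concern.** The treatment rule joins two end conditions with an *or*, and the first is a symptom. Symptoms can ease before glucose recovers. A subject could then stop treatment while still hypoglycemic by the section's own bands, and nobody would be required to check. The subjects carry injected basal and bolus insulin plus an added oral insulin, so the glucose-lowering drive may still be present. This is a patient-safety matter before it is a statistical one.

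The stopping count raises a separate, lesser question. It is the only mandatory per-subject hypoglycemia count, and it is tied to the visit, whereas most dosing happens at home. If it means episodes that occur during a visit, it is close to inert. If it means episodes reported at a visit, it is a different rule, and sites could apply it differently.

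**Working it through.** **1. The treatment rule, case by case.** No arithmetic applies; the question is when each wording lets treatment end.

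| State after tablets | Section 7.3.1 as written | Ending on a repeat glucose above 70 |
|---|---|---|
| Symptoms gone, glucose above 70 | may end | ends |
| Symptoms gone, glucose 70 or below | may end | continues |
| Symptoms gone, glucose not measured | may end | measure first |
| Symptoms persist, glucose above 70 | may end | tablet rule met; symptoms left to clinical judgment |
| Symptoms persist, glucose 70 or below | continues | continues |

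The second and third rows are the gap. Nothing in 7.3.1 limits how low glucose may be in the second row; it could lie in the mild band or lower. The documents do not say how often symptoms resolve before glucose does, so the size of the gap cannot be computed.

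**2. The schedule behind the count.** The plan's own figure reproduces: Day 56 − Day (−21) = 77 days, as the synopsis states. The same subtraction gives randomized dosing of 56 − 1 = 55 days (51 to 59 with the ±2-day windows), with four visits after Day 1.

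**3. How much the count covers if read literally.** Assumption: each visit lasts 3 hours (the documents give no length). Time covered is 4 × 3 = 12 hours out of 55 × 24 = 1,320 hours, or 0.9%.

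**4. Chance that the literal count triggers.** Assumption: symptomatic episodes follow a Poisson process at *r* per week. The documents give no rate, so a range is shown.

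- Mean per visit: m = r × 3/168.
- Chance of 3 or more in one visit: p = 1 − e^(−m)(1 + m + m²/2).
- Chance over four visits: P = 1 − (1 − p)⁴.

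For r = 1: m = 0.0179, p ≈ 9.4 × 10⁻⁷, P ≈ 3.7 × 10⁻⁶.

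| Episodes per week | Expected in 55 days (r × 55/7) | P, same rate for all | P, strong variation between subjects (gamma, shape 0.5) |
|---|---|---|---|
| 0.25 | 2.0 | 5.9 × 10⁻⁸ | 8.7 × 10⁻⁷ |
| 0.5 | 3.9 | 4.7 × 10⁻⁷ | 6.8 × 10⁻⁶ |
| 1 | 7.9 | 3.7 × 10⁻⁶ | 5.2 × 10⁻⁵ |
| 2 | 15.7 | 3.0 × 10⁻⁵ | 3.8 × 10⁻⁴ |

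The largest entry is 0.038%. With a common rate of up to 4 per week and 4-hour visits, P is 5.4 × 10⁻⁴, still about 0.05%. Counting Visit 3 as a fifth visit does not change the picture.

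**The case against.** **The tablet text leaves room for a recheck.** It says tablets are given as necessary, and nothing forbids a second reading. Exclusion 2 keeps out subjects with a documented glucose of 50 mg/dL or less without symptoms at Screening. Section 6.3.6 says staff will be advised on nocturnal hypoglycemia. These points lower the risk, but none requires a repeat glucose, and the content of that advice is not given. Section 7.3.2 does require a repeat reading for hyperglycemia, but that reading decides withdrawal and is not a treatment end point. The comparison shows only that repeat readings are already part of the protocol.

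**Home episodes are not unguarded.** A reader might infer that hypoglycemia between visits goes unseen or cannot be acted on. The documents do not support that. Section 7.4 has subjects report all adverse events and be assessed throughout. Both lists in Section 4.3 apply wherever the event happens. The protocol diary covers insulin and carbohydrate "over the 10-day CGM monitoring period of each treatment period", but SAP Section 2.7.2 takes hypoglycemia from a separate log whose listing (16.2.7.2) is not labelled as limited to the final 10 days. What is absent is a mandatory number for home episodes; judgment fills that place. This objection stands.

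**A mandatory home count is not clearly better.** A reader might go on to infer that the protocol needs one. Hypoglycemic episodes are the first secondary objective, and forced removal would cut short the outcome being compared. Section 4.3 adds "Randomized subjects who are discontinued from this study for any reason will not be replaced", and the early-withdrawal procedure in Section 3.9 ends with "Discharge from the study". As an illustration, at an assumed 0.25 counted episodes a week, withdrawal after more than 2 in any rolling 7 days would remove 4-11% of subjects over 55 days (simulation). Reading the present count as episodes reported at Visits 4 to 6 would remove 6-12%. The two are close. Both rest on assumed rates, and the second rests on a reading the text does not state, so they show a trade-off and are not evidence of harm.

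**Sections 4.3 and 7.3.1 do not conflict.** One lists hypoglycemia as a discretionary reason to stop study drug; the other mandates ending participation at a count. A reader might call this a contradiction, but the two actions can coexist.

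**Conclusion.** The treatment point holds on the text alone and needs no assumed rate: as written, tablets may stop with glucose still below 70 mg/dL and no repeat reading. Its frequency is unknown from the documents, but the correction is cheap enough not to depend on it.

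The count is a secondary matter of clarity. Read literally, it almost never triggers: below 0.04% per subject for 0.25 to 2 episodes a week and 3-hour visits, all assumed. It cannot detect repeated episodes at home. Those remain a matter for the investigator under Section 4.3, which is a defensible design in subjects with type 1 diabetes who adjust their own insulin. The sponsor should say what the phrase means. The documents do not show that a compulsory home-count withdrawal is needed.

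**What to change.** In Section 7.3.1:

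1. **Treatment end condition (main change).** Replace the two alternatives with one: tablets continue until a repeat blood glucose is above 70 mg/dL. Leave symptoms that persist above 70 mg/dL to clinical judgment. The cost is one extra fingerstick per treated episode. At the assumed 0.25 to 2 episodes a week, if every episode is treated, that is about 2 to 16 per subject over 55 days, in a population for whom Section 1 describes glucose self-monitoring as usual care.
2. **Stopping count (clarification).** State whether the count refers to episodes occurring during a visit or reported at one. This costs a few words.
3. **Optional.** Ask sites to refer repeated symptomatic episodes at home promptly to the medical monitor for review, without automatic withdrawal. The cost is one protocol sentence and a call when it applies. If the sponsor prefers a mandatory home count, its period and glucose threshold should be chosen with the likely removals and lost crossover data in view.
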